8. TRIAL DESIGN

8.1. Description of Study Design

A schedule of procedures and assessments is displayed in [Section 4](#).

This will be a multicenter, randomized, double-blind, parallel group study comparing tranexamic acid (test) to placebo (control) for reduction of perioperative blood loss after complex spinal fusion surgery (defined as spinal fusion surgery in the T2 to Pelvis/Sacrum area involving more than 4 Functional Spinal Units (4 discs/motion segments=5 Vertebral segments)). In addition to test and control treatments, all patients undergoing spinal fusion surgery will receive anesthesia and standard of care for blood loss including colloid/crystalloid fluid replacement and packed red cells, if necessary, according to a common multi-institutional protocol. Anesthesia will keep the mean arterial pressure as low as safe for the patient during exposure of surgery (estimated at 60-80 MAP). Patients will be randomized to receive either 30 mg/kg tranexamic acid loading dose as a one hour infusion (3 mL/kg) prior to start of procedure and as an infusion at 3 mg/kg/h (0.3 mL/kg/h) of tranexamic acid throughout the surgery in the test group; or, a one hour infusion at 3 mL/kg of 0.9% saline prior to start of the procedure and an infusion of 0.9% saline at 0.3 mL/kg/h in the control group. The maximum dose will be 50 mg/kg.

The active phase of the study will be for the duration of hospital stay postoperatively for efficacy measurements and at 6 weeks for safety follow-up. The randomization will be open only to the statistician generating the randomization sequence. All PI(s), study conduct and monitoring staff, as well as the subjects will be completely blinded to the treatments except in the case of emergency. An analyzable patient is one who satisfies admission criteria and who completes all required assessments.

8.2. Study Endpoints

8.2.1. Primary Endpoints

The primary endpoints of this trial are to assess:

1. Total Blood Loss based on changes in hemoglobin (Blood loss will be calculated by Nadler's and Gross's formulae from the time of admission to hospital until discharge; Hemoglobin and hematocrit concentrations will be measured pre-operatively, post-operatively, and at 24 h and every 24h thereafter until discharge).
2. Incidence of autologous or allogenic blood transfusion, including red blood cells and coagulation components (such as fresh frozen plasma and platelets).

8.2.2. Secondary Endpoints

The Secondary endpoints include assessment of:

1. Total Measured Blood Loss (measured intra-operatively and for up to 24 hours post-operatively and every 24 hours up to discharge when the two subfascial drains are removed). Total Measured Blood Loss will be estimated as 3 times cell saver.
2. Number of patients with symptomatic anemia (such as tachycardia, hypotension, presyncope) of <8.0 g/dL hemoglobin, or any hemoglobin <7.0 g/dL, precipitated transfusion. *[Alternatively, allogenic blood transfusion will be considered for hemoglobin <9 g/dL intraoperatively or <8 g/dL post-operatively]*
3. Number of patients with adverse events related to tranexamic acid such as confirmed deep vein thrombosis (DVT), pulmonary embolism (PE), or seizures.
4. Other outcomes will include functional recovery, duration of hospital stay, and wound complications (infections, hematomas, and other complications related with surgery).

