6.3. Potential Risks and Benefits

6.3.1. Known Potential Risks²

Visual abnormalities, often poorly characterized, represent the most frequently reported postmarketing adverse reaction in Sweden. No retinal changes have been reported or noted in eye examinations in patients treated with tranexamic acid for weeks to months in clinical trials.

Convulsions have been reported in association with tranexamic acid treatment, particularly in patients receiving tranexamic acid during

cardiovascular surgery and in patients inadvertently given tranexamic acid into the neuraxial system.

Ureteral obstruction due to clot formation in patients with upper urinary tract bleeding has been reported in patients treated with tranexamic acid.

Gastrointestinal disturbances including nausea, vomiting, and diarrhea may occur but disappear when the dosage is reduced. Allergic dermatitis, giddiness and hypotension have been reported occasionally. Hypotension has been observed when intravenous injection is too rapid. To avoid this response, the solution should be not be injected more rapidly than 100 mg/min.

Thromboembolic events such as deep vein thromboses (DVTs) and pulmonary embolism (PE) are associated with tranexamic acid use.

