10.7.2. Classification of an Adverse Event

The Principal Investigator will evaluate all AEs as follows:

Seriousness: whether or not the AE is fatal or life threatening, persistent or permanently disabling, requires or prolongs inpatient hospitalization, is a congenital anomaly or an important medical event or requires medical intervention to prevent one of the above outcomes

Action taken: whether or not the AE caused the subject to discontinue the study drug, or use a concomitant medication

Intensity, to be graded as:

DEGREE	DESCRIPTION
Mild	Awareness of signs and symptoms; easily tolerated
Moderate	Discomfort sufficient to interfere, but not prevent daily activity
Severe	Unable to carry out usual activity

Relationship to study drug, to be graded as:

DEGREE	DESCRIPTION
Not related	The experience is clearly related to other factors such as the subject's clinical state, therapeutic interventions or concomitant drugs administered to the subject.
Unlikely	The experience was most likely produced by other factors such as the subject's clinical state, therapeutic interventions or concomitant drugs administered to the subject which do not follow a known response pattern to the trial drug.
Possible	The experience follows a reasonable temporal sequence from the time of drug administration, and/or follows a known response pattern to the trial drug, but could have been produced by other factors such as the subject's clinical state, therapeutic interventions or concomitant drug administered to the subject.
Probable	The experience follows a reasonable temporal sequence from the time of drug administration, and follows a known response pattern to the trial drug, and cannot be reasonably explained by other factors such as the subject's clinical state, therapeutic interventions or concomitant drugs administered to the subject

Related
	
The experience follows a reasonable temporal sequence from the time of drug administration, and follows a known response pattern to the trial drug, and cannot be reasonably explained by other factors such as the subject’s clinical state, therapeutic interventions or concomitant drugs administered to the subject, and either occurs immediately following trial drug administration, or improves on stopping the drug, or reappears on repeat exposure, or there is a positive reaction at the application site.

----------------	---

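### Secondary endpoint 3 is worded as events related to tranexamic acid with no causality cut-off, so it may undercount DVT, PE and seizures; it should count them whatever the cause

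*Combined protocol and SAP*

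**What the plan says.** Secondary endpoint 3 appears in the same terms in the synopsis (objectives and endpoints), in 8.2.2 and in 10.5: "Number of patients with adverse events related to tranexamic acid such as confirmed deep vein thrombosis (DVT), pulmonary embolism (PE), or seizures".

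Section 10.7.2 gives causality grading to the site: "The Principal Investigator will evaluate all AEs as follows". The scale has five levels:

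- *Not related* and *Unlikely* point to other causes. *Unlikely* is limited to factors such as "clinical state, therapeutic interventions or concomitant drugs administered to the subject which do not follow a known response pattern to the trial drug".
- *Possible* covers an event that has a reasonable time relation to dosing and/or "follows a known response pattern to the trial drug, but could have been produced by other factors".
- *Probable* and *Related* both require that the event "follows a known response pattern to the trial drug, and cannot be reasonably explained by other factors".

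Section 6.3.1 lists the events concerned as known risks: "Thromboembolic events such as deep vein thromboses (DVTs) and pulmonary embolism (PE) are associated with tranexamic acid use", and "Convulsions have been reported in association with tranexamic acid treatment".

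Other sections deal with the same events without a causality condition. Footnote 7 to the schedule explains the row on tranexamic acid related complications as thromboembolic symptoms, with imaging confirmation, and any seizure seen in hospital. Section 10.3.4 follows these events daily in hospital and at 6 weeks. Section 10.7.4 documents every adverse event, related or not. Section 11.4.4 compares the arms by Fisher exact test on patients with each adverse event category. Section 11.4.3, which names the secondary variables to be analysed, does not mention endpoint 3.

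**The concern.** On its plain wording the endpoint is filtered by attribution. Every subject has just had a long multilevel fusion, which is a reasonable alternative explanation for a DVT or PE. A site that applies the 10.7.2 scale with care could seldom grade such an event Probable or Related. The count would then depend on a cut-off that the plan does not state and on the attribution habits of eight sites.

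A randomised, double-blind, placebo-controlled trial does not need this filter, since the comparison of arms already separates drug effect from surgical background. At stake is the named endpoint for the known thromboembolic and seizure risks, in a trial that section 7 says will support registration. It could show few cases, or none, while the all-cause counts differ between arms.

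**Working it through.** **Is there a figure in the plan to reproduce?** Not for this endpoint. The documents give no rate for DVT, PE or seizure and no share expected to be judged related. The sample size of 128 in 11.2 concerns blood loss and does not enter here.

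**Step 1. What each possible cut-off does to a postoperative DVT or PE.**

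| Events counted as related | Test in 10.7.2 | Likely result |
|---|---|---|
| Probable or Related | Other factors cannot reasonably explain the event | Few qualify, because the operation is a reasonable explanation |
| Possible and above | Fits timing and/or a known drug pattern, even if other factors could explain it | Most may qualify, because 6.3.1 lists DVT and PE as known risks |
| No filter (footnote 7 reading) | None | All confirmed events count |

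Convulsions are also listed in 6.3.1, so a seizure too can fit Possible. The endpoint can therefore run from nearly empty to nearly complete on a choice that the plan leaves open.

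**Step 2. Size of the loss if a filter applies.** Let *q* be the share of patients with an event who remain counted, taken as equal in both arms because assessors are blinded (8.1). Let *p*T and *p*C be the true all-cause risks, with 100 drug and 50 placebo patients (section 5).

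- Expected counts: 100 × *p*T × *q* and 50 × *p*C × *q*
- Risk difference: *q* × (*p*T − *p*C)
- Risk ratio: (*q* × *p*T) / (*q* × *p*C) = *p*T / *p*C, so *q* cancels

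All rates and values of *q* below are assumptions. Power is the exact power of the two-sided 5% Fisher test.

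| Assumed risks (drug vs placebo) | *q* | Expected counts | Risk difference (points) | Risk ratio | Fisher power |
|---|---|---|---|---|---|
| 4% vs 2% | 1 | 4.0 vs 1.0 | 2.0 | 2 | 1.0% |
| | 0.5 | 2.0 vs 0.5 | 1.0 | 2 | 0.2% |
| | 0.25 | 1.0 vs 0.25 | 0.5 | 2 | 0.1% |
| 6% vs 2% | 1 | 6.0 vs 1.0 | 4.0 | 3 | 5.6% |
| | 0.5 | 3.0 vs 0.5 | 2.0 | 3 | 0.3% |
| | 0.25 | 1.5 vs 0.25 | 1.0 | 3 | 0.1% |
| 10% vs 2% | 1 | 10.0 vs 1.0 | 8.0 | 5 | 32.9% |
| | 0.5 | 5.0 vs 0.5 | 4.0 | 5 | 3.9% |
| | 0.25 | 2.5 vs 0.25 | 2.0 | 5 | 0.1% |

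**Step 3. Chance that the endpoint shows no case in either arm.** This is (1 − *q* × *p*T)^100 × (1 − *q* × *p*C)^50. At 6% vs 2% and *q* = 0.25 it is 0.985^100 × 0.995^50 = 17.2%. With all events counted it is 0.1%.

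**The case against.** The strongest reply is that the phrase is a label for a class of events and not a filter. Footnote 7 defines the schedule row of nearly the same name without any causality condition. Section 10.3.4 plans surveillance for events described in the same way, and surveillance cannot be limited to events already judged causal. The words *such as* leave the list open, and nothing links endpoint 3 to the 10.7.2 scale. This stands as a possible reading, but it does not settle the matter: those places govern follow-up and recording, while 8.2.2 governs the count and says related.

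A reader might infer that the scale allows most DVT, PE and seizures to be put down to the operation. The documents do not support that. *Unlikely* is confined to factors that do not follow a known drug pattern, and all three events are listed as known risks, so *Possible* fits them. No figure in the documents supports the word *most*.

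A reader might also infer that the trial's safety comparison is lost. It is not: all adverse events are documented, and 11.4.4 compares them by arm without a filter. That section does not state the MedDRA level, however, and does not promise a combined DVT/PE count, so it does not replace a well-defined endpoint.

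Finally, power is low even with every event counted (5.6% at 6% vs 2%). That is correct. The gain from the change is a complete and interpretable count, not a decisive test.

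**Conclusion.** The point holds as a defect of definition in one secondary endpoint. Its wording is a causality condition without a stated cut-off, and it does not match how footnote 7 records the same events. If the cut-off were Probable or higher, counts and risk difference would shrink to the share kept, and power would fall with them. If Possible counts, the loss may be small.

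The sizes rest on assumed event rates and assumed shares kept; the documents supply neither. The unchanged risk ratio rests on blinded assessors attributing events alike in both arms. The documents show a possible undercount in endpoint 3. They do not show that an undercount will occur, that it would be large, or that the all-cause comparison in 11.4.4 is affected.

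**What to change.** 1. In the synopsis, 8.2.2 and 10.5, define endpoint 3 as the number of patients with confirmed DVT, confirmed PE or seizure from the start of the first infusion to the 6-week visit, regardless of the investigator's assessment of relationship.
2. List the endpoint in 11.4.3 with a between-arm comparison for DVT/PE combined and another for seizures. State the test: Cochran-Mantel-Haenszel, which that section provides for low incidences, or Fisher exact as in 11.4.4.
3. Align footnote 7, which limits seizure recording to the hospital stay, with the 6-week window that 10.3.4 already uses for these events.
4. Keep the causality grades, and other events suspected to be drug-related, as descriptive listings, so that closing the open list loses nothing.

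The cost is wording. Section 10.7.4 already documents all adverse events and 10.3.4 already follows these ones to 6 weeks, so no new type of data is needed. The downside for the sponsor is that the reported count may look less favourable.

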8.3. Study Population

8.3.1. Inclusion Criteria

Subjects must meet the following inclusion criteria:

1. All adult patients (Male or Female) over age eighteen (>18) electively undergoing complex spinal fusion surgery (defined as T2 to Pelvis/Sacrum and greater than 4 Functional Spinal Units (4 discs/motion segments=5 Vertebral segments).
2. Female subjects of childbearing potential with a negative serum (beta human chorionic gonadotropin [HCG]) pregnancy test at screening and urine pregnancy test at each admission; who are not breastfeeding; do not plan to become pregnant during the course of the study; and agree to use an approved method of birth control, such as condoms, foams, jellies, diaphragm, intrauterine device, sexual abstinence for at least 3 months prior to study;
3. Able to provide written informed consent after risks and benefits of the study have been explained;
4. Able to communicate effectively with study personnel.

8.3.2. Exclusion Criteria

Subjects meeting any of the following criteria will be excluded from the study:

1. History or presence of any clinically significant (based on the Investigator's judgment) cardiovascular, respiratory, metabolic, hepatic, gastrointestinal, renal, hematological, dermatological, neurological, or psychiatric disease or condition preventing the use of tranexamic acid as described in this protocol;
2. History of renal failure or elevated creatinine above 1.4;
3. Any diagnosis of spinal tumor or intradural pathology;

4. Diagnosis of ankylosing spondylitis;
5. History or presence of acquired disturbance of color vision;
6. History of seizures;
7. History of thromboembolic event (DVT or PE) within the past year
8. Current use of anticoagulant medications or past medical history leading to an abnormal coagulation profile preoperatively;
9. Subjects diagnosed with fibrinolytic disorders requiring intra-operative antifibrinolytic treatment; hematological disease (thromboembolic events, hemoglobinopathy, coagulopathy, or hemolytic disease).
10. Significant drug sensitivity or significant allergic reaction to any drug, including tranexamic acid, based on the Investigator's judgment;
11. A subject who has donated or lost 450 mL or more blood volume (including plasmaphoresis) or had a transfusion of any product within 3 months prior to the initial study drug administration.
12. Pre-operative anemia (hb <110 in females, Hb <120 in males);
13. Any subject that chooses to refuse blood products for ethical or religious purposes (Jehovah's Witness);
14. Current participation in a drug or other investigational research study or participation within 30 days prior to the initial study drug administration.
15. A subject who may not be able to comply with the safety monitoring requirements of this clinical trial or is considered by the investigator, for any reason, to be an unsuitable candidate for the study.

16. Intraoperative cardiovascular, pulmonary, orthopedic, or anesthetic complication such as myocardial infarction, intraoperative fracture, vasopressor support or emergent intubation.
17. Female patients who are using combination hormonal contraception.
18. Patients with history of subarachnoid hemorrhage.
19. Patients with serum creatinine above ULN.

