8.4. Randomization and Blinding

When the subjects meet admission criteria and provide written informed consent, they will receive a subject number and be randomized by subject number into one of two treatment arms. They will receive either tranexamic acid or normal saline according to the randomization schedule. The randomization schedule will be generated prior to study initiation by a statistical programmer. The pharmacy will perform and document the randomization.

Subjects will be treated according to a randomization schedule prepared prior to the start of the study. The investigator site personnel as well as Exela personnel involved in the monitoring or conducting of the trial will be blinded to the trial drug codes (or kit codes), except in the case of an emergency. Trial drug codes will not be available to the above personnel until after the completion of the trial and final data review.

An individual decoding unit containing emergency identification of the kit contents will be provided for each kit.

- i. This decoding unit must not be opened unless an actual emergency occurs. The investigator should also make a careful note of the date, time of opening, and the reason.
- ii. In the event that a decoding unit is opened, the Exela monitor must be notified immediately by the investigator.
- iii. At the conclusion of the trial, all decoding units are to be returned to Exela together with unused drug supplies.

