10.3.3. Drug Dosing

Blinded treatments will be administered at an initial dose of 3 mL/kg as a one hour infusion using a calibrated infusion pump prior to start of procedure, and as a 0.3 mL/kg/h infusion during surgery up to a maximum infusion volume of 5 mL/kg. Each treatment will be administered by a calibrated infusion pump. The pump's manufacturer, model, and serial number will be recorded on the CRF. The volume infused remains constant regardless of whether the patient is receiving tranexamic acid or saline.

At the termination of the trial, all unused trial medication must be returned to Exela Pharma Sciences. Instructions for the return of trial medication will be provided by Exela at the completion of the trial.

Blood samples for hemoglobin measurement will be collected prior to start of procedure, at the end of the procedure, at 24 h, and every 24 h thereafter until discharge. Hematocrit analysis will also be conducted on all collected blood samples.

The following data will also be recorded:

- Treatment ID
- Details of surgical procedure [Number of vertebrae fused, number of anchors used, and type of anchors used (screws, hooks, or anchors); Number and type of osteotomies performed]
- Any complication prolonging the surgery time or increasing patient blood loss
- Surgery time
- Estimated blood loss peri-operatively (from drainages and absorbent/surgical pads)
- Volume of cell saver delivered
- Units of autologous transfusion and allogenic transfusion
- Units of fresh frozen plasma and platelets administered
- Volume of crystalloids/colloids given
- Urine output
- Location of Hemovac drains and number of drains placed
- Drain output recorded daily
- Length of drain use (uniformly remove drains when output <120 mL/day)
- Length of hospital stay
- Complications of autologous or allogenic transfusion
- Complications of tranexamic acid including renal, hepatic, thromboembolic, and brain/CNS
- Functional recovery assessments will be completed prior to discharge
- Any wound complications for the duration of hospitalization

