10.3.5. Final Study/Early Termination Visit

Subjects who complete the study will have procedures collected as described in Period 2. If a subject withdraws early from the study, the same information will be collected as follows:

- a. A final physical examination will be done.
- b. Sitting vital signs blood pressure, pulse, and temperature will be obtained.
- c. Specimens for safety laboratory tests will be obtained.
- d. The subject will be asked if he/she had any adverse experiences.

If a subject withdraws from the study at any time, either at his or her request or at the Principal Investigator's discretion, the reason(s) for withdrawal will be recorded on the relevant page of the source. All final visit tasks (discharge procedures) will be completed for all subjects who withdraw from the study. Withdrawn subjects may be replaced at the Sponsor's discretion. Subjects withdrawn due to AEs will be monitored until resolution or stabilization of the AE or until 30 days from the initial report of the AE, whichever occurs first.

If a subject is discontinued, the following consistent terminology will be used to capture this information on the CRF:

- Death
- Lost to Follow-up
- Adverse Event
- Non-Compliance with Study Drug
- Physician Decision
- Protocol Violation
- Study termination by Sponsor
- Withdrawal of Consent

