11.3. Populations for Analysis

Up to approximately 150 patients will be enrolled.

The primary analysis population will be a modified Intent to Treat (mITT) population consisting of all subjects receiving an injection of TXA or Placebo.

The secondary analysis population will be a Per Protocol (PP) population consisting of all subjects without major protocol violations (to be

determined by a blinded committee prior to breaking the double-blind code).

The safety population will consist of all subjects receiving an injection of TXA or placebo.

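### Exclusion item 16 names intraoperative complications, which arise after randomisation; it conflicts with Section 11.3 and, if enforced, may cost dosed patients their 24 h primary measurement

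*Combined protocol and SAP*

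**What the plan says.** All references are to the combined protocol and SAP.

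- **Section 8.3.2** opens its list with "Subjects meeting any of the following criteria will be excluded from the study". Item 16 of that list is "Intraoperative cardiovascular, pulmonary, orthopedic, or anesthetic complication such as myocardial infarction, intraoperative fracture, vasopressor support or emergent intubation".
- **Section 8.4** sets the order of events: "When the subjects meet admission criteria and provide written informed consent, they will receive a subject number and be randomized by subject number".
- **Section 10.3.3** gives the loading dose "as a one hour infusion using a calibrated infusion pump prior to start of procedure". It also lists, among the data to record, "Any complication prolonging the surgery time or increasing patient blood loss".
- **Section 11.3** defines the primary population as a "modified Intent to Treat (mITT) population consisting of all subjects receiving an injection of TXA or Placebo" and adds: "The safety population will consist of all subjects receiving an injection of TXA or placebo". Neither sentence makes an exception. A blinded committee decides which protocol violations remove a subject from the Per Protocol set.
- **Section 8.1** calls a patient analyzable only if the admission criteria are met and every required assessment is completed.
- **Section 10.3.5** says "All final visit tasks (discharge procedures) will be completed for all subjects who withdraw from the study" and lets the sponsor replace withdrawn subjects.
- **Section 11.4.2** makes the 24-hour blood loss the primary measure. Section 10.5 computes it from the hematocrit before and after surgery.

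**The concern.** An exclusion list is meant to be checked before a patient is randomised. Item 16 cannot be, because it describes events during surgery. Taken literally, it tells a site to exclude from the study a patient who has been randomised and usually already dosed. Section 11.3 tells the statistician to analyse that same patient.

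The main stake is the primary measurement. A site that regards a patient as excluded has no clear instruction to obtain the 24 h hematocrit, and Section 11 gives no method for missing values. If the reasons for leaving depend on blood loss or on treatment, the patients with a 24 h value are no longer the groups that randomisation formed.

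**Working it through.** **1. Timing.** The order is eligibility and consent, randomisation (8.4), one-hour loading infusion before the procedure (10.3.3), surgery. An intraoperative event therefore always follows randomisation. It normally follows the loading infusion too. The protocol does not time that infusion against induction of anesthesia, so an event at induction could overlap or precede it.

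**2. Who is analysed.** For a dosed patient with an intraoperative complication:

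| Text | What it implies |
|---|---|
| 8.3.2, item 16 | excluded from the study |
| 8.1, analyzable patient | not analyzable if admission criteria are read to include item 16, or if an assessment is missed |
| 10.3.3 | the complication is recorded as study data |
| 11.3 | in the mITT and safety sets |

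The withdrawal criteria (8.3.3), the early-termination text (10.3.5) and Section 11 do not mention item 16. Sections 12.3 and 12.4 were not in the copy reviewed.

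**3. What is measured.** A withdrawn subject still has the discharge procedures (10.3.5), and Section 4 schedules blood collection at discharge. Section 10.5 also allows a discharge hematocrit in the formula. A later value is therefore likely to exist; the 24 h value that 11.4.2 makes primary is not assured.

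**4. Could leaving depend on outcome or treatment?** For vasopressor support it could. Section 8.2.2 names hypotension as a sign of symptomatic anemia, and 6.3.1 lists it among occasional reactions to tranexamic acid. Intraoperative fracture, by contrast, need not depend on either.

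**5. Arithmetic.** Section 11.2 assumes 2000 against 1500 mL, SD 1000 mL, two-sided 5% and 80% power. A two-sample t-test needs 63.77, rounded up to 64 per group, or 128. The loss allowance is (150 − 128)/150 = 14.7%. Both stated figures reproduce. They assume equal groups; at the planned 100:50, power is 81.8%.

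The documents give no removal rate. The following uses assumed removals and is no estimate or bound.

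- *Unrelated to blood loss, equal in both arms:* the expected difference stays at 500 mL and power falls from 81.8% to 79.8% (5% removed) or 77.6% (10%).
- *All patients above a cut-off c removed, normal losses:* the mean of those left is μ − σφ(a)/Φ(a), with a = (c − μ)/σ. For c = 3500 mL, control is 2000 − 1000 × 0.1295/0.9332 = 1861 and TXA is 1500 − 1000 × 0.0540/0.9772 = 1445. The difference is 416 mL, with 6.7% and 2.3% removed. For c = 3000 mL it is 1712 − 1361 = 351 mL.
- *Same 3500 mL cut-off, TXA arm only (a drug-related trigger):* 2000 − 1445 = 555 mL.

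The difference can shrink, stay the same or grow.

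**The case against.** The strongest reply is that Section 11.3 is explicit. Leaving the study and leaving an analysis set are different things, and on its plain wording every dosed patient is analysed whatever item 16 says. That stands as far as set membership goes. A reader might infer that item 16 takes these patients out of the primary analysis and so will bias it. The documents do not support that: bias may follow, and only if the item is enforced and measurements are lost. Membership of the mITT, however, does not supply a missing 24 h value.

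A reader might also infer that events such as myocardial infarction would vanish from the safety comparison. The safety set is all dosed subjects, and AE and SAE reporting (10.7) still applies, so that inference fails on the text.

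Three further objections have force.

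- Section 6.3.1 also links hypotension to injection faster than 100 mg/min. The loading dose runs at 30/60 = 0.5 mg/kg/min and reaches that rate only at 100/0.5 = 200 kg, so that sentence is weak support here. The separate mention of occasional hypotension remains. Section 8.1 also has anesthesia keep arterial pressure low in every patient, which is a source of vasopressor use unrelated to treatment.
- The synopsis omits item 16, but it omits other exclusions too, such as the history of seizures, so the omission proves little.
- The item may have a clinical purpose that the text does not state. A call simply to delete it would decide a question that the documents leave open.

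**Conclusion.** The concern holds in a conditional form and should be fixed. Item 16 cannot operate as an eligibility criterion, it contradicts Section 11.3, and the definition of an analyzable patient in Section 8.1 adds to the conflict. That much follows from the text alone.

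The consequence depends on conduct. If sites keep following these patients and Section 11.3 governs, only contradictory wording remains. If sites enforce the item, the 24 h value may be lost in dosed patients for reasons that may depend on bleeding or treatment, and the blood-loss comparison may be biased. Size and direction cannot be estimated, because the protocol gives no complication or removal rate; the illustrative figures rest wholly on assumed removal patterns.

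**What to change.** Reconcile Sections 8.3.2 and 11.3, with matching sentences in 8.1 and 10.3.5:

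- State that item 16 is not an eligibility criterion, and that meeting it does not remove a randomised, dosed subject from follow-up, from the mITT set (analysed as randomised) or from the safety set.
- State that the 24 h and daily hemoglobin and hematocrit, the transfusion data and the 6-week safety assessment are still collected unless consent is withdrawn.
- State that the definition of an analyzable patient in 8.1 does not narrow the mITT, and that replacing a withdrawn subject under 10.3.5 does not take a dosed subject out of it.
- Handle complicated cases in the blinded Per Protocol review or in a sensitivity analysis.

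If item 16 has a clinical purpose, such as stopping the infusion, the sponsor should state it separately. No clinical rule is proposed here.

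The cost is a small amendment of a few sentences and slightly more outcome variability from retained complicated cases. Section 13 records that exclusion criteria were added in version 1.3 on FDA comments without saying which. The sponsor should check where item 16 came from, since the change may then need regulatory discussion.
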